16.0 CHANGES TO ANALYSES SPECIFIED IN PROTOCOL

This SAP amendment includes additional analyses listed below. There are no other changes to the analyses specified in the final Protocol Amendment 2 (version dated 12 Oct 2018) and Amendment 3 (version dated 20NOV2018).

- Prior ADT use in current episode recorded on ATRQ (Section 7)
- Weight adjusted dose of rapastinel (section 8.4)

Appendix II. Pattern-Mixture Model Details

For repeated measures under monotone missing, the pattern-mixture model with non-future dependent missing assumption proposed by Kenward et al (2003) provides a feasible solution to accommodate certain missing not at random (MNAR) mechanism. The methodology relies on constructing unidentifiable conditional densities using identifiable densities and borrows techniques from standard multiple imputation.

1. Non-Future Dependent Missing Assumption

Assume there are T designed visits in a longitudinal study and let $y_i (i = 1, 2, \dots, T)$ represent patient's measurement at Visit i . When the missing is monotonic, the pattern of missing *data* can be defined by the number of measurements (L) actually observed from the patient. Let $f(y_1, \dots, y_j | L = t)$ denote the conditional density of y_1, \dots, y_j , given *that* the last observed measurement at Visit t . Then the overall density function for Pattern t can be written as

$$f(y_1, \dots, y_T | L = t) = f(y_1, \dots, y_t | L = t) f(y_{t+1} | y_1, \dots, y_t, L = t) \times \prod_{s=t+2}^T f(y_s | y_1, \dots, y_{s-1}, L = t) \quad (1)$$

Note on the right hand side of (1) the first factor is clearly identifiable from the observed data, while the second and the beyond are not, due to lack of available data. The second factor $f(y_{t+1} | y_1, \dots, y_t, L = t)$ could be identifiable based on an assumed relationship between $f(y_{t+1} | y_1, \dots, y_t, L = t)$ and $f(y_{t+1} | y_1, \dots, y_b, L \geq t+1)$. The third and beyond factors $f(y_s | y_1, \dots, y_{s-1}, L = t)$ (with all $s \geq t+2$) could be identifiable with the help of non-future dependent missing assumption.

For longitudinal data with dropouts, non-future dependent missing (NFD) (Kenward, 2003) assumes that the unidentifiable conditional distributions of $y_s (s \geq t+2)$, *given earlier measurements*, in Pattern t , *is set to be equal to the corresponding distribution in pattern $L > s-1$* :

$$f(y_s | y_1, \dots, y_{s-1}, L = t) = f(y_s | y_1, \dots, y_{s-1}, L \geq s-1) \quad (2)$$

The right hand side of (2) can further be partitioned into

$$f(y_s | y_1, \dots, y_{s-1}, L \geq s-1) = \sum_{j=s-1}^T \omega_{s-1,j} \cdot f(y_s | y_1, \dots, y_{s-1}, L = j) \quad (3)$$

where mixture probabilities $\omega_{s-1,j}$ are

$$\omega_{s-1,j} = \frac{\alpha_j f(y_1, \dots, y_{s-1} \mid L = j)}{\sum_{t=s-1}^T \alpha_t f(y_1, \dots, y_{s-1} \mid L = t)}, \text{ and } \alpha_j \text{ represents the fraction of patients from Pattern } j. \quad (4)$$

Each factor of the unidentifiable conditional distribution of y_s ($s \geq t + 2$) on the right side of (1) can be expressed using the following:

- $f(y_s \mid y_1, \dots, y_{s-1}, L = s - 1)$, the unidentifiable conditional distribution of the first missing in pattern $s-1$,
- $f(y_s \mid y_1, \dots, y_{s-1}, L = j)$, the identifiable conditional distributions of y_s given y_1, \dots, y_{s-1} of pattern j ($j \geq s$), and
- α_j , the fraction of patients from pattern j ($j \geq s - 1$).

So under NFD, all the unidentifiable conditional distributions on the right side of (1) can be estimated and missing values could be therefore imputed based on the assumption for unidentifiable conditional distribution of the first missing **value**.

We re-formulate the partition in (3), for $s \geq t + 2$, as the following:

$$f(y_s \mid y_1, \dots, y_{s-1}, L = t) = \delta_{s-1} f(y_s \mid y_1, \dots, y_{s-1}, L = s - 1) + (1 - \delta_{s-1}) f(y_s \mid y_1, \dots, y_{s-1}, L \geq s) \quad (5)$$

for $s \geq t + 2$ with $\delta_{s-1} = \omega_{s-1,s-1}$.

Therefore, under monotone missing and NFD assumption, the unidentifiable conditional densities for Visit s in Pattern t ($s \geq t + 2$) can be expressed as a mixture distribution of $f(y_s \mid y_1, \dots, y_{s-1}, L = s - 1)$ - the unidentifiable conditional distribution of the first missing measurement y_s in Pattern $s - 1$, and $f(y_s \mid y_1, \dots, y_{s-1}, L \geq s)$ - the identifiable conditional distribution of y_s from all the patterns with observed data at Visit s or beyond:

$$f(y_s \mid y_1, \dots, y_{s-1}, L \geq s) = \sum_{j=s}^T \lambda_{s-1,j} f(y_s \mid y_1, \dots, y_{s-1}, L = j) \quad (6)$$

where the mixture probability

$$\lambda_{s-1,j} = \omega_{s-1,j} / (1 - \omega_{s-1,s-1}) =$$

$$\frac{a_j f(y_1, \dots, y_{s-1} | L = j)}{\sum_{t=s}^T a_t f(y_1, \dots, y_{s-1} | L = t)} \text{ for } j \geq s, \text{ where } a_j \text{ is the fraction of } \\ \text{patients from Pattern } j. \quad (7)$$

The conditional densities for the first missing are selected as:

$$f(y_s | y_1, \dots, y_{s-1}, L = s-1) = f(y_s - \Delta | y_1, \dots, y_{s-1}, L \geq s) \text{ for } s = 2, \dots, T, \quad (8)$$

Note that the two distributions only differ from a shift (Δ) parameter. When $\Delta = 0$, the missing value y_s in Pattern $s-1$ is imputed based on the distribution of all observed data up to Visit s , as a result, leading to missing at random (MAR) missingness. When $\Delta \neq 0$, (8) will introduce a scenario of MNAR. A similar idea was also presented in the recent publication “*The Prevention and Treatment of Missing Data in Clinical Trials*” by the National Academy Press. The selection of the plausible values for the shift parameter (Δ) is discussed in Section 3.

Note that per recommendation in Wang and Daniels (2011), only the observed data within the pattern is assumed to be multivariate normal. The observed data distribution can be expressed in terms of the marginal distribution of baseline measurements and the conditional distributions of postbaseline measurements given earlier measurements. Assuming that these distributions are normal, the linear regression of each observation on prior observations will yield least-squares estimates of model parameters that can be utilized for independent posterior draws of model parameters for observed data. The multiple imputation approach will be used to estimate the overall mean at the final time point.

2. Imputation Procedure

All the missing data will be imputed to create a complete dataset, then statistical analysis can be performed using appropriate techniques such as **MMRM**. The imputation **can accommodate MNAR missing data mechanisms**, based on the theory discussed in the above sections.

The model parameters for each dropout pattern, i.e., the mean, variance and proportions of observations in each pattern, are drawn from their posterior distributions prior to the imputation of missing data for a single imputation.

The details of imputation within a pattern, say Pattern t , are as the following:

Step 1. Impute the first missing value y_{t+1} for each patient in Pattern t ($t = 1, \dots, T-1$):

- a. Compute estimates of mixture probabilities $\lambda_{s-1,j}$ in (7) with $s = t+1$ given the posterior draw of proportions of observations in each pattern and the posterior draw of regression parameters for the observed data.
- b. Draw a random integer from $\{s, \dots, T\}$ to index a component distribution on the right hand side of (6), using mixture probabilities obtained in a). Draw y_{t+1}^* from the identified component normal distribution. Impute the missing y_{t+1} as $\tilde{y}_{t+1} = y_{t+1}^* + \Delta$.

Step 2. Impute the rest of the missing values of $y_{t+2}, y_{t+3}, \dots, y_T$ for patients in Pattern t:

Starting with imputation for y_{t+2} , first, similar to Step 1, draw y_{t+2}^* from the normal mixture (6) based on the observed y_1, \dots, y_t and the already imputed \tilde{y}_{t+1} for the patient. Then the missing y_{t+2} is imputed as $\tilde{y}_{t+2} = y_{t+2}^* + \Delta$ with probability δ_{t+1} and as $\tilde{y}_{t+2} = y_{t+2}^*$ with probability $1 - \delta_{t+1}$, where the mixture probability $\delta_{t+1} = \omega_{t+1,t+1}$ is obtained from (4) given the posterior draw of proportions of observations in each pattern and the posterior draw of regression parameters for the observed data.

Missing values of y_{t+3} through y_T can be imputed similarly as y_{t+2} .

To summarize, the imputations of y_{t+1} through y_T is done recursively within each Pattern t (for all $t = 1, \dots, T - 1$) to create a complete dataset after imputation is done for all patterns with missing values.

The above imputation procedure is applied to all subjects in each missing data pattern to create a single imputed data set. Repeating the process of drawing parameters from the posterior distribution and imputing missing data given the posterior draw m times will yield m imputed data sets. The observed or imputed values at the final data point are averaged to obtain the overall mean estimate for each imputed data set, and the multiple imputation estimate is obtained by averaging the estimates across m imputations.

In this sensitivity analysis, m is set to equal to 20. The value of m is discussed in the context of imputation efficiency in standard multiple imputation theory (Rubin, 1987, p. 114), and $m = 20$ would provide at least 96% of relative efficiency as compared with using an large number of imputations (SAS/STAT User's Guide, p. 3796).

3. Determination of the Shift Parameter Values

The common shift parameter Δ is the difference between the mean of y_{t+1} among those who drop out at Visit t and those who remain beyond Visit t ($1 \leq t \leq T - 1$). The exact value of Δ is unknown and can't be estimated from data because of missingness. The magnitude of Δ depends on the medical aspects of the trial. Using relevant historical data, one may select Δ as a proportion of the sample standard deviation or a proportion of observed treatment efficacy.

RESTRICTED

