While the study was ongoing, the primary efficacy variable was revised to be the change from baseline in MADRS score at the last visit, Day 21, and the primary efficacy study population was revised to include all randomized patients (placebo responders and placebo non-responders) based on the feedback by the FDA, EMA, and PDMA. Both of these changes were included in Amendment 2 of the protocol. At the same time of Amendment 2, a blinded data review was conducted for Studies RAP-MD-01, RAP-MD-02, and RAP-MD-03. The pooled SD for the three studies were 7.4, 8.0, and 8.7, respectively, all smaller than the originally assumed 10 points. Sample size was re-calculated using 8.7 as the common SD. The calculation used MMRM model with simulations; it also assumed correlation of 0.5 between the repeated measures and a common drop-out rate of 10% during the randomized treatment period and an additional 5% drop-out rate during the placebo lead-in period for all treatment groups. To have 90% power, the total sample size required is 360 patients. However, the study had already enrolled more than 440 patients with less than 5% of overall drop-out rate, surpassing the re-estimated sample size of 360 patients. The study enrollment was halted as soon as operationally feasible. The final sample size is approximately 460 patients (230 patients per treatment group).

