14.0 STATISTICAL SOFTWARE

Statistical analyses will be performed in [REDACTED]

RESTRICITED

15.0

DATA HANDLING CONVENTIONS

15.1

VISIT TIME WINDOWS

Table 15.1–1 presents visits assigned and the corresponding range of treatment days (window) during which an actual visit may occur for all safety analyses where baseline is the last nonmissing assessment before the first dose of DB IP in the placebo lead-in period. The visit windows used in the “change from Day 0” or “reduction from Day 0” efficacy analyses will be derived according to this table as well. Termination visit is assigned to the visit window according to the table below.

Table 15.1–1. **Visit Time Windows for Change from Day 0 in Efficacy and Change from Baseline in Safety Analyses**

Analysis Visit	Target Date	Analysis Window (Based on Date)
Baseline	Index0 ^a	Last record on or before Index0 ^a
Day 1	Index0 ^a +1	Index0 ^a +1
Day 4	Index0 ^a +4	[Index0 ^a +2, IndexA ^b -1]
Day 7	IndexA ^b	IndexA ^b
Day 8 ^d	IndexA ^b +1	IndexA ^b +1
Day 11	IndexA ^b +4	[IndexA ^b +2, IndexB ^c -1]
Day 14	IndexB ^c	IndexB ^c
Day 15 ^d	IndexB ^c +1	IndexB ^c +1
Day 18	IndexB ^c +4	[IndexB ^c +2, IndexB ^c +5]
Day 21 ^{de}	IndexB ^c +7	Days [IndexB ^c +6, day of final double-blind visit or Early-termination Visit occurring after IndexB ^c +5]
Day 28	IndexB ^c +14	Within the safety follow-up phase

a Index0: Date of placebo dose during the placebo lead-in period

b IndexA: Date of first randomized dose or Index0 + 7 for patients who did not receive any randomized dose

c IndexB: Date of second randomized dose or IndexA + 7 if the 2nd dosing of randomized treatment was not administered for patients who were randomized

d For analysis of parameters

the visit windows for Days 1 and 8 will be extended to cover the next dosing day (indexA and indexB, respectively); the visit window for Day 15 will be 1 day after IndexB to Day 19; and the visit window for Day 21 will be Days 20 to the last double-blind visit, inclusively.

For efficacy analysis where baseline is defined as the last measurement prior to the first dose of randomized IP, the assigned visit and the corresponding range of treatment days (window) during which an actual visit may occur is displayed in **Table 15.1–2**. Termination visit is assigned to the visit window according to the table below.

Table 15.1–2. Visit Time Windows for Change from Baseline in Efficacy Analyses

Analysis Visit	Target Date	Analysis Window (Based on Date)

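### Does the pattern-mixture sensitivity analysis need a stated rule for dropout patterns too small to fit?

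*SAP*

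**What the plan says.** SAP 9.1 plans one sensitivity analysis for the missing-at-random assumption. It is a pattern-mixture model with patterns defined by the last observed visit and a shift of 0 to 8 points. Appendix II gives the algorithm.

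- **Model.** The observed data are factored into "the marginal distribution of baseline measurements and the conditional distributions of postbaseline measurements given earlier measurements", and "linear regression of each observation on prior observations will yield least-squares estimates of model parameters".
- **Parameters.** "The model parameters for each dropout pattern, i.e., the mean, variance and proportions of observations in each pattern, are drawn from their posterior distributions".
- **Step 1.** A missing score at visit s is drawn from one component of equation (6). The component is picked at random from patterns s to T with the weights in (7), and the shift is then added.
- **Step 2.** Later missing scores are drawn the same way. The shift is added only with a probability that "is obtained from (4) given the posterior draw of proportions of observations in each pattern" and of the regression parameters.
- **Zero shift.** The missing score "is imputed based on the distribution of all observed data up to Visit" s.

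SAP 13.0 reports that "the study had already enrolled more than 440 patients with less than 5% of overall drop-out rate" and gives a final size of about 460. SAP Table 15.1-2 lists Days 8, 11, 14, 15, 18 and 21 after baseline. SAP 2.0 says the SAS code was moved to a separate document, and Appendix II ends in restricted text.

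**The concern.** A regression within a pattern needs more patients than it has coefficients. Dropout is so low that the later patterns, which have the most predictors, may hold only a handful of patients. Appendix II shows no minimum pattern size, no pooling rule and no informative prior, and does not say whether fits are by arm. SAP 9.1, by contrast, sets out a full sequence of fallbacks if the MMRM fails to converge.

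This is the only visible check of missing-at-random behind the primary result. If the written procedure cannot be run, someone must choose a substitute, possibly after seeing the data. That would matter if the choice could move the answer.

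**Working it through.** **Yardstick.** The design difference is 3.25 points (SAP 13.0, given for the original design and assumed unchanged). With SD 8.7, 90% power and two-sided 0.05, n per arm = 2 × (1.960 + 1.282)² × 8.7² / 3.25² = 150.6, so 151. Dividing by 0.85 gives 178 per arm, or 356 in total, against the stated 360. The figure reproduces.

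**How many dropouts.** 5% × 460 = 23, so below 5% means at most 22. Lead-in dropouts are not in the mITT Population, so the relevant number may be smaller. Completers: 460 − 22 = 438.

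**What separate fits would need.** Assume MADRS at all six visits and a flat prior. Number the patterns t = 1 to 5 for a last score on Day 8, 11, 14, 15 or 18. A fit in pattern t needs t + 2 patients with baseline as a predictor and t + 1 without. Empty patterns and the lowest occupied pattern need no fit. With all five occupied the minimum is 1 + 4 + 5 + 6 + 7 = 23 with baseline, or 1 + 3 + 4 + 5 + 6 = 19 without.

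**Chance that every needed fit exists.** Multinomial simulation, 300,000 draws, arms pooled. The spread over visits is not in the documents, so several were tried.

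| Spread of 22 dropouts | With baseline | Without |
|---|---|---|
| Even | 0.3% | 2.8% |
| Proportional to visit gaps (3:3:1:3:3) | 1.0% | 4.8% |
| Early (5:4:3:2:1) | 0.9% | 3.1% |
| Late (1:2:3:4:5) | 4.1% | 19.9% |
| Days 8, 11, 18 only | 61% | 79% |
| Days 11, 18 only | 97% | 99% |

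With 11 dropouts the last two rows fall to 1.7% / 7.0% and 27% / 50%. So non-estimable fits are likely under most spreads, though not all.

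**Where a dropout component can enter.** At Day 21, s = T and the index set s to T contains only T. Every imputed Day 21 value is therefore drawn from the completers' regression. A dropout component can affect Day 21 only through an imputed intermediate score or through the probability of an additional shift.

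**How often.** Approximate the weights in (4) and (7) by pattern fractions. For the even spread each pattern holds 22 / 5 = 4.4 patients.

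- Imputed values per dataset: 4.4 × (5 + 4 + 3 + 2 + 1) = 66.
- Draws from a dropout component, Days 11, 14, 15 and 18: 4.4 × 17.6/455.6 + 8.8 × 13.2/451.2 + 13.2 × 8.8/446.8 + 17.6 × 4.4/442.4 = 0.17 + 0.26 + 0.26 + 0.18 = 0.86 (from unrounded terms). At Day 21 it is 0.
- Additional shifts, Days 14, 15, 18 and 21: 4.4 × 4.4/455.6 + 8.8 × 4.4/451.2 + 13.2 × 4.4/446.8 + 17.6 × 4.4/442.4 = 0.04 + 0.09 + 0.13 + 0.18 = 0.43 (from unrounded terms).

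| Spread | Imputed values | Dropout-component draws | Additional shifts |
|---|---|---|---|
| Even | 66 | 0.86 | 0.43 |
| Gap-proportional | 66 | 0.92 | 0.42 |
| Early | 81 | 0.74 | 0.41 |
| Late | 51 | 0.74 | 0.41 |
| Days 8, 11, 18 | 73 | 0.96 | 0.36 |
| Days 11, 18 | 55 | 0.81 | 0.27 |

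**Size.** Largest shift, all in one arm, carried in full to Day 21: 0.43 × 8 / 230 = 0.015 points. If every dropout-component draw were also displaced by a whole SD in one arm and carried in full: 0.96 × 8.7 / 230 = 0.036 points. The sum is about 0.05, or 1.6% of 3.25. Doubling every weight gives about 0.1. Fewer dropouts shrink both terms.

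**The case for a change.** The strongest case for a change is that the equations do call for pattern components. If all patterns shared one regression, picking a component at random would do nothing. Failure is foreseeable at the reported dropout, and by arm it is near certain: with 11 dropouts per arm and three or more patterns, the chance that all fits exist is below 0.5%. The MMRM has stated fallbacks, this analysis shows none, and the remedy would be a few lines of text.

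Much of that stands: the rule is not visible, and the arithmetic on pattern sizes is right. Three things limit it.

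- **Separate slopes are not settled by the wording.** The parameter list names a mean, a variance and a proportion, and SAP 9.1 states the linear relation once per visit. With common slopes a pattern needs about 2 patients, and the chance that all fits exist at 22 dropouts rises to 53% to 84% over five patterns and 99.7% for Days 8, 11 and 18. It is lower with fewer dropouts.
- **An even five-way spread is not the natural expectation.** In SAP 15.1, "Termination visit is assigned to the visit window according to the table below". Days 8, 14 and 15 have single-day windows, while Days 11 and 18 span several days and would collect many of these visits.
- **The fallback has little leverage.** Pooling patterns, sharing slopes or adding a weak prior would alter fewer than one imputed intermediate score per dataset on average. Fitting by arm makes sparsity worse but leaves the pattern fractions, and so the weights, about the same.

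Replacing the components with one regression per visit and redefining the shift probability would depart from the cited method for no material change in the result.

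**Conclusion.** No change is needed. Appendix II leaves open how to handle a pattern too small to fit, and that situation is likely under most dropout spreads. It is a missing detail in a sensitivity analysis, of the kind analysts fill sensibly, and the programming document or the restricted text may already fill it. The effect is about 0.015 MADRS points through additional shifts, and about 0.05 on a deliberately harsh reckoning, against 3.25. The primary MMRM does not use these fits.

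This rests on at most 22 dropouts, MADRS at all six post-randomization visits, an assumed set of dropout spreads, and mixture weights approximated by pattern fractions. Actual weights also depend on patients' scores, so the sizes are approximate. That Day 21 values are drawn only from the completers' regression follows from the SAP's equations and does not depend on the spread.

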9.1 PRIMARY EFFICACY PARAMETER

The primary efficacy parameter will be the change from baseline to Day 21 in MADRS total score for the mITT population. The MADRS total score is the sum of the 10 individual items. If more than 2 items are missing, then the total score will be set to missing. If there are multiple assessments of MADRS total score for the same nominal visit of a patient, only the last assessment will be used in the analysis.

The primary efficacy parameter will be analyzed using a mixed model for repeated measures (MMRM) with treatment group, pooled study center, visit, placebo responder status at Day 7, and treatment group-by-visit interaction as the fixed effects, and Day 0 MADRS total score, baseline MADRS total score, Day 0 MADRS total score-by-visit and baseline MADRS total score-by-visit interactions as covariates. An unstructured covariance matrix is used to model the covariance of change in scores within patients. The Kenward-Roger approximation will be used to estimate denominator degrees of freedom ([Kenward et al, 1997](#)). The analysis will be performed based on all post-randomization data using only the observed cases without imputation of missing values.

In the case that the MMRM model with unstructured covariance fails to converge with the default algorithm, then the Fisher scoring algorithm will be used to provide better initial values of the covariance parameters; if the model still does not converge, a simplified model without term for study center will be used to find the initial values of the covariance parameters. In the rare event that the model still does not converge after using those initial values, simplified covariance structures will be used to fit the model in the following order until the model converges: (1) ante-dependence, (2) heterogeneous autoregressive, (3) Toeplitz, and (4) compound symmetry.

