To assess the robustness of the primary MMRM results to the possible violation of the missing-at-random assumption, a sensitivity analysis using a pattern-mixture model based on non-future dependent missing value restrictions (Kenward et al, 2003) will be performed. The pattern for the pattern-mixture model will be defined by the patient's last visit with observed value. The observed MADRS total score at a visit is assumed to have a linear relationship with the patient's prior measurements. The missing values will be imputed under the assumption that the distribution of the missing observations differs from the observed only by a shift parameter value Δ . The dataset with missing values will be analyzed using the same model as the primary analysis for between-treatment group comparisons. The imputation of missing values and the analysis will be performed multiple times and the inference of this sensitivity analysis will be based on the combined estimates using the standard multiple imputation technique. The values for Δ will be selected as 0 to 8.

[figure not shown]

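### The missing-not-at-random sensitivity analysis shows one shift with no arm-specific value, so it says little about rapastinel dropouts alone doing worse

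*SAP*

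**What the plan says.** Protocol 9.7.5.1 and SAP 9.1 plan a pattern-mixture analysis to check the primary MMRM against departures from missing-at-random. Patterns are defined by the last visit with an observed score, and treatment arm plays no part in that definition. The shift values "will be selected as 0 to 8"; no arm is named.

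SAP Appendix II gives the mechanics:
- Equation (8), introduced by "The conditional densities for the first missing are selected as", sets the distribution of the first missing score equal to that of patients still observed, displaced by one quantity Δ.
- Steps 1 and 2 add Δ at the first missing visit. At each later visit they add it again only with a mixture probability δ.
- On scope: "The above imputation procedure is applied to all subjects in each missing data pattern to create a single imputed data set".
- Section 3 calls the quantity "The common shift parameter" and defines it by dropping out versus remaining.
- On the imputation models, "the linear regression of each observation on prior observations will yield least-squares estimates of model parameters". Treatment is not mentioned.

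The primary MMRM, by contrast, has "treatment group-by-visit interaction as the fixed effects". On analysing the imputed data, SAP 9.1 says: "The dataset with missing values will be analyzed using the same model as the primary analysis for between-treatment group comparisons".

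SAP 13.0 reports more than 440 patients enrolled "with less than 5% of overall drop-out rate". That figure is pooled and not split by arm.

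**The concern.** A positive rapastinel result would be weakened if patients who leave the rapastinel arm fare worse than their earlier scores predict, while placebo dropouts do not. A shift applied equally to both arms does not pose that question. It raises the imputed Day 21 mean in each arm, and with similar dropout the two increases cancel. Where dropout differs, the move can even favour rapastinel, if that arm has fewer dropouts or dropouts whose shift carries less to Day 21.

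No other missing-data check is visible for the primary endpoint, although parts of the SAP after 9.2 are blacked out. A reader could take stability over shifts 0 to 8 as evidence of robustness when it is largely a property of the design.

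A second, conditional point concerns a shift of 0. If the imputation regressions pool the arms without a treatment term, imputed scores are pulled towards the common mean, and even that run would differ somewhat from the primary analysis.

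**Working it through.** **Inputs.** From SAP 13.0: 230 per arm, SD 8.7 (this study's own blinded SD was 7.4), correlation 0.5, dropout below 5%. From SAP Table 15.1–2: six post-randomization visits, Days 8, 11, 14, 15, 18 and 21. The 3.25-point difference is stated in current text for the plan of 700 patients; carrying it to the re-estimation is an assumption. Dropout of 5% per arm is used as an upper value and 2% as an assumed lower one.

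**The plan's own figure.** The documents give no number for this sensitivity analysis, so the inputs were checked on sample size. Per arm, n = 2 × (1.960 + 1.282)² × 8.7² / 3.25² = 150.6, so 151. Then 151 / 0.85 = 178 per arm, or 356 in total, against 360 stated.

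**Algebra.** Let d be an arm's dropout rate and c the average fraction of the shift that reaches Day 21. The Day 21 difference moves by

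ΔR × dR × cR − ΔP × dP × cP.

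With ΔR = ΔP this is Δ × (dR·cR − dP·cP), which is zero when dropout matches in rate and timing.

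**Carry-through.** Take exchangeable correlation 0.5, 5% dropout spread evenly over last visits Day 8 to Day 18 (1% each), and δ as the simple pattern share. With k earlier visits each regression coefficient is 0.5 / (1 + 0.5(k − 1)). For a patient last seen at Day 15, the Day 18 score gets the full shift, and Day 21 gets 1/6 + 0.01/0.96 = 0.18 of it. For last visits Day 8, 11, 14, 15 and 18 the fractions are 0.35, 0.26, 0.21, 0.18 and 1.00, with mean 0.40. A rapastinel-only shift of 8 therefore moves the difference by 8 × 0.05 × 0.40 = 0.16. Correlations of 0.3 to 0.9 give 0.14 to 0.18. If every dropout were last seen at Day 18, c = 1 and the bound is 8 × 0.05 = 0.40.

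**Simulation.** 10,000 replicates, 20 imputations, 230 per arm, true difference −3.25, sequential regressions by arm, SD 8.7 unless stated. Day 21 estimates:

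| Dropout, rapastinel / placebo | Shift 0 | 8 in both arms | 8 in rapastinel only |
|---|---|---|---|
| 2% / 2% | −3.25 | −3.25 | −3.19 |
| 5% / 5% | −3.25 | −3.25 | −3.09 |
| 5% / 5%, SD 7.4 | −3.26 | −3.26 | −3.10 |
| 4% / 6% | −3.24 | −3.30 | −3.11 |
| 6% / 4% | −3.26 | −3.19 | −3.07 |
| 5% / 5%, rapastinel last seen Day 18, placebo Day 8 or 11 | −3.25 | −2.97 | −2.86 |
| 5% / 5%, timing reversed | −3.23 | −3.52 | −3.12 |

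Before rounding, the common-shift moves in the last four rows are 0.07 in rapastinel's favour, 0.06 against, 0.28 against and 0.28 in favour.

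**Effect on significance (SD 8.7).** At 5% dropout the mean |z| is 3.94 at shift 0, 3.92 with the common shift and 3.74 with rapastinel only. Of significant results, the share that loses significance at shift 8 is:
- all significant results: 0.2% common versus 1.3% rapastinel-only at 5% dropout; 0.2% versus 0.4% at 2%.
- those with p of 0.01 to 0.05 at shift 0 (about 600 of 10,000): 3% versus 21% at 5% dropout; 3% versus 7% at 2%.

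**Where it would matter.** SE = 8.7 × √(2/230) = 0.81. With the t quantile 1.965 (458 degrees of freedom) the significance limit is 1.59, and 1.59 + 0.16 = 1.75. Observed differences of about 1.59 to 1.75 (p about 0.05 to 0.03) would lose significance on average. With SD 7.4 the SE is 0.69 and the range is 1.36 to 1.52.

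**Treatment in the imputation.** Pooling the arms without a treatment term shrinks the shift-0 estimate by 0.05 at 5% dropout and 0.02 at 2%.

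**The case against.** The strongest objection is that Appendix II is a generic one-sample account. Nothing in it carries a treatment index, and it ends in an overall mean, although SAP 9.1 requires a comparison of arms. The missing index is therefore weak evidence of equal shifts. In Section 3, the word common may mean common across visits. In the reviewed copy that section stops at a restriction mark, and the History of Changes places the code in a separate document. This stands, and it is why the point is conditional. It does not alter what SAP 9.1 and Steps 1 and 2 visibly state.

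The effect is also small at the reported dropout, and the 21% figure concerns only about 6% of replicates. Both are correct.

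The 0.40 bound is remote. Protocol 9.1.2 and 9.3.3 ask for Visit 11 assessments from dosed patients and early terminators, and SAP Table 15.1–2 assigns late termination visits to Day 21. Many late dropouts would thus not be missing at Day 21. This stands.

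The simulation is not the planned analysis. It uses one regression per visit in place of mixture (6), a simple share for δ, and a raw Day 21 mean difference without the MMRM covariates. The sizes are therefore approximate, but the cancellation is algebraic and does not depend on them.

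Finally, fitting the pattern-specific regressions separately by arm is not workable. Dropout of 5% in 460 patients is 23 people; over five patterns and two arms that is about 2.3 each. Nor would it make shift 0 equal the MMRM. Both stand, and the fix avoids that route.

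**Conclusion.** The point holds in conditional form, as a minor improvement. No arm-specific shift is visible. If one shift serves both arms, the analysis responds only to between-arm differences in dropout rate or timing and says little about rapastinel dropouts alone doing worse than missing-at-random predicts.

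Three stronger readings are not supported:
- A reader might infer that the plan definitely uses equal shifts. Withheld text or code could say otherwise.
- A reader might infer that the primary conclusion is in doubt. At 3.25 points, the extreme rapastinel-only shift leaves about 3.09 at 5% dropout and 3.19 at 2%, both far above the limit of about 1.59.
- A reader might take 0.40 points as the likely loss. It is a theoretical bound that needs every dropout to be last seen at Day 18.

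What remains is a borderline result, with p about 0.03 to 0.05 at 5% dropout. The sizes assume dropout spread evenly over visits, exchangeable correlation and the simplified simulation. The 5% is probably high for the mITT analysis, since the reported figure is below 5% and may include lead-in dropouts.

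**What to change.** In SAP 9.1 and Appendix II:
- State whether the shift is the same in both arms. If an arm-specific rule already exists, saying so settles the main point.
- Keep the common-shift run as supportive. Add runs over the same 0 to 8 range with the shift applied to rapastinel dropouts only (placebo shift 0), or a two-way grid of arm-specific shifts.
- Report the shift, if any, at which significance is lost.
- Include treatment as a term in the imputation regressions, rather than fitting pattern-specific regressions separately by arm. Shift 0 will then be close to the primary MMRM, though not identical to it.

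The cost is a few sentences, a treatment term in the imputation code and some further runs, best specified before unblinding. The downside is a slightly less favourable sensitivity estimate at the extreme shift of 8: about 0.06 points at 2% dropout and 0.16 at 5%. With dropout this low, the added runs will usually find no shift at which significance is lost.
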